#### 12.1.1.1. ≥ 20% Reduction in PS volume

PS volume reduction at each 12-week interval compared to the baseline of the core study TED-C13-003 will be calculated using average daily values. The number and percentage of subjects who achieve at least a 20% reduction in PS volume (mL/kg/day) at each 12-week interval during the retrospective observation period will be summarized.

#### 12.1.1.2. Change and percent change from baseline in PS volume and intake calories

Changes and percent change are calculated following common calculations in Section 7.5. The baseline is defined as the PS prescribed data collected at the baseline of the core study TED-C13-003.

#### 12.1.1.3. Change and percent change from baseline in hours per day and days per week of PS

Change and percent change from baseline in hours per day and days per week of PS during retrospective observation period will be summarized using the non-missing prescribed value using descriptive statistics.

### 12.1.2. ANALYSES OF EFFICACY VARIABLES

For the variables of pre-specified % reduction in PS volume, the number and percentage of subjects will be presented by interval and treatment group. Baseline values, post-baseline values, change from baseline and percent change from the baseline in PS will be summarized by interval and treatment group using descriptive statistics including number of subjects, mean, standard deviation, median, minimum and maximum.

---

Document: \\quintiles.net\Enterprise\Apps\sasdata\SASa\sas\Shire\Teduglutide\ZXA48914\Biostatistics\Documentation\Protocol\SHP633-303\_Retrospective\_SAP\_Final\_V1.0\_20171013

Author: [REDACTED] Version Number: Final V1.0  
Version Date: 13Oct2017

Template No: CS\_TP\_BS016 – Revision 3  
Effective Date: 01May2012

Reference: CS\_WI\_BS005

Copyright © 2012 Quintiles Transnational Corp. All rights reserved.  
The contents of this document are confidential and proprietary to Quintiles Transnational Corp. Unauthorized use, disclosure or reproduction is strictly prohibited.

## 13. STUDY DRUG EXPOSURE

The extent of exposure is defined as the number of days on teduglutide during the core study and retrospective observation period combined. Exposure summary will be presented by treatment group (TED/NTT, TED/TED and ANY TED) as a numeric variable. It will also be categorized and presented in pre-defined groups: 0-<12, 12-<24, 24-<48, 48-<72, 72-<96, >=96 weeks.

### 13.1. DERIVATIONS

The extent of exposure in weeks will be calculated as:

Extent of exposure (weeks) = [the exposure days in the core study calculated as (last dose date – first dose date + 1) + the sum of all the teduglutide prescription durations during the retrospective period where the individual duration is calculated by (prescription stop date – prescription start date +1)] / 7.

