To evaluate efficacy and safety from the time subjects completed the core study to the time they enter this extension study, retrospective data collection is planned for this study. The retrospective data collection will consist of specific safety and efficacy measures that were completed in the course of the subject's standard medical care between the date of the TED-C13-003 end of study (EOS), which is the final scheduled visit 4 weeks after the end of treatment, and the date the ICF (and if applicable, informed assent) is signed for this study. Retrospective PS and growth data will be captured in 12-week intervals, with the first 12-week interval beginning at the TED-C13-003 EOS. All available retrospective data should be captured in the corresponding electronic case report forms (eCRFs). The following data will be collected:

- Teduglutide use (as prescribed)
- Parenteral support (as prescribed)
- Growth (height, head circumference [up to 36 months of age], weight)
- End dates for adverse events (AEs) ongoing at the time of TED-C13-003
- All nonserious AEs related to teduglutide
- All adverse events of special interest (AESIs)
- All serious adverse events (SAEs)

In addition to this retrospective data collection, prospective study assessments of safety and efficacy will be completed as a part of this study. The prospective data analysis will be described in the prospective SAP for this study.

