## 8.3. MISSING DATA

Missing data will in general not be imputed. All available data will be included in the safety analysis.

Document: \\quintiles.net\Enterprise\Apps\sasdata\SASa\sas\Shire\Teduglutide\ZXA48914\Biostatistics\Documentation\Protocol\SHP633-303\_Retrospective\_SAP\_Final\_V1.0\_20171013  
Author: [REDACTED] Version Number: Final V1.0  
Version Date: 13Oct2017

Template No: CS\_TP\_BS016 – Revision 3  
Effective Date: 01May2012

Reference: CS\_WI\_BS005

Copyright © 2012 Quintiles Transnational Corp. All rights reserved.  
The contents of this document are confidential and proprietary to Quintiles Transnational Corp. Unauthorized use, disclosure or reproduction is strictly prohibited.

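### The retrospective exposure formula sums prescription lengths, so it counts shared days twice and gives no duration for a prescription still open at consent

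*SAP*

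**What the plan says.** In the retrospective SAP, Section 13 gives the definition: "The extent of exposure is defined as the number of days on teduglutide during the core study and retrospective observation period combined". The result is summarised by treatment group as a number and in the categories "0-<12, 12-<24, 24-<48, 48-<72, 72-<96, >=96 weeks".

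Section 13.1 gives the formula. The core-study part is "the exposure days in the core study calculated as (last dose date – first dose date + 1"). The retrospective part is "the sum of all the teduglutide prescription durations during the retrospective period where the individual duration is calculated by" an inclusive day count for each record, and the formula closes with "prescription stop date – prescription start date +1)] / 7".

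Three other places bear on it:

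- Section 4.1 lists the drug data collected as "Teduglutide use (as prescribed") and ends the retrospective period on "the date the ICF (and if applicable, informed assent) is signed for this study".
- Section 8.3 states "Missing data will in general not be imputed".
- Section 12.1.1 starts the first 12-week interval on the day after the core end-of-study (EOS) date.

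The retrospective SAP has no rule for merging records, for counting a shared date once, or for ending a prescription that is still running at consent. The partial-date appendix in the same file, with its reference end date, belongs to the separate prospective SAP.

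**The concern.** The defined quantity is a count of days. The derived quantity is a sum of interval lengths. A sum equals a count only when the intervals are disjoint and closed, and the SAP states neither condition.

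The two departures pull in opposite directions. Shared days inflate exposure. A prescription with no stop date has no length, so a programmer must choose between dropping the record, setting the child's total to missing, or cutting the record at the ICF date. These choices give different results, and the first two take time away from children who were still on the drug at consent. Retrospective safety and tolerability is the primary objective of this interim analysis, and the exposure table is what tells the reader how much time on drug lies behind the safety data.

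**Working it through.** The SAP states no numerical exposure result, so there is no figure to reproduce. The check applies the Section 13.1 formula to assumed prescription patterns and compares it with a count of distinct days.

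**Inputs from the SAP:** the formula (Section 13.1), the categories (Section 13), and the end of the period at the ICF (Section 4.1).

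**Assumed inputs (not in the documents):** 84 core days, and the prescription dates below, with day 1 = core EOS + 1.

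**Formulas**

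- SAP: weeks = [core days + Σ(stop − start + 1)] / 7
- Distinct days: weeks = [core days + number of calendar days covered by at least one prescription] / 7

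Core and retrospective days should not overlap, because the retrospective period starts at the core EOS, 4 weeks after the end of treatment.

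**Closed prescriptions**

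| Pattern (days) | SAP formula | Distinct days | Excess |
|---|---|---|---|
| One record, 1–168 | (84 + 168)/7 = 36.00 | 36.00 | 0 days |
| Next-day renewal, 1–84 and 85–168 | (84 + 84 + 84)/7 = 36.00 | 36.00 | 0 days |
| Same-date hand-over, 1–84 and 84–168 | (84 + 84 + 85)/7 = 36.14 | 36.00 | 1 day |
| 14-day overlap, 1–98 and 85–168 | (84 + 98 + 84)/7 = 38.00 | 36.00 | 14 days |
| 28-day overlap, 1–112 and 85–168 | (84 + 112 + 84)/7 = 40.00 | 36.00 | 28 days |
| Two fully concurrent records, 1–168 twice | (84 + 168 + 168)/7 = 60.00 | 36.00 | 168 days |

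The excess equals the number of shared days. Only the last row changes category here, from 24-<48 to 48-<72 weeks. One shared day is enough at a boundary: records 1–84 and 84–251 give (84 + 84 + 168)/7 = 48.00 weeks by the formula, against (84 + 251)/7 = 47.86 by distinct days, and so fall on different sides of the 48-week limit.

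**Prescription open at the ICF, started on day 1**

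The formula has no stop date to use and returns no value. If the record is dropped, only the core days remain: 84/7 = 12 weeks, category 12-<24. If the record is cut at the ICF on day D, the total is (84 + D)/7:

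| ICF day D | Weeks | Category |
|---|---|---|
| 84 | 24 | 24-<48 |
| 168 | 36 | 24-<48 |
| 252 | 48 | 48-<72 |
| 336 | 60 | 48-<72 |
| 504 | 84 | 72-<96 |

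Under these assumptions, every ICF day shown gives a different category from the dropped record.

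**The case against.** The strongest reply is that the formula is right for ordinary records. Stop minus start plus 1 is the correct length of a closed interval, and disjoint intervals add up to days on drug. This stands. A reader might infer that all back-to-back prescriptions are double counted, but the next-day renewal in the table shows no excess.

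Nor do the documents show that overlaps or open records occur. Section 12.1.1 describes the use period as running from prescription start to prescription stop and mentions the beginning and end of any teduglutide treatment. That fits one record per treatment course at least as well as one per refill. This also stands, and it makes the sizes above illustrations rather than estimates.

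On the open end, the formula refers to durations during the retrospective period, and ending a record at the ICF is censoring, not imputation. A cut at the ICF is therefore a natural reading, and Section 8.3 does not oblige anyone to drop the record. But no truncation step is written, and no end date is supplied for an ongoing prescription. The natural reading is a reason to write the rule down.

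Three further inferences go too far:

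- **Overlap always moves a child to another category.** It need not: 36 and 38 weeks are both in 24-<48.
- **A child on an open prescription has no exposure.** The core days still count if only the open record is dropped.
- **The safety percentages are distorted.** Section 14.1 summarises adverse events by number and percentage of subjects, and Appendix 1 makes the number of subjects the default denominator. Section 6.1 assigns treatment groups by any use, not by duration. No hypothesis is tested (Section 8.4).

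**Conclusion.** The point holds as a mismatch between definition and derivation. Section 13.1 does not always deliver the number of days that Section 13 defines. It over-counts by exactly the days that two records share, and it leaves the retrospective duration undefined for a prescription without a stop date at the ICF.

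The open prescription matters more: in the illustration, 12 weeks against 24 to 84 weeks, compared with 2 weeks for a 14-day overlap. Both figures rest on the assumed 84 core days and assumed prescription dates. How often either case arises cannot be told from the documents. The effect is confined to the descriptive exposure summary and its categories, so this is an inexpensive clarification and does not threaten the interim's conclusions.

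**What to change.** In Section 13.1 of the retrospective SAP, replace the sum of prescription durations with the number of distinct calendar days, from core EOS + 1 (the start already used in Section 12.1.1) to the ICF date inclusive, that are covered by at least one teduglutide prescription. State that, for this calculation, a prescription ongoing at the ICF or with a later stop date ends on the ICF date. Leave the core-study part and the division by 7 as they are. Add a footnote to the exposure table that retrospective days are prescribed days, not confirmed dosing days.

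The cost is a few sentences of SAP text and a short programming step that merges date ranges. No new data are needed. Where records are disjoint and closed within the period, the result is unchanged.

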## 14. SAFETY OUTCOMES

There will be no statistical comparisons between the treatment groups for safety data.

### 14.1. ADVERSE EVENTS

Adverse Events collected during the retrospective observation period will be coded using **Medical Dictionary for Regulatory Activities (MedDRA) central coding dictionary, Version 19.1**. Investigator verbatim as well as preferred terms and system organ classes will be included in the listings.

An overall summary of number of subjects within each of the categories described below will be provided as specified in the templates. Adverse events that occurred during the retrospective observation period will be summarized using descriptive statistics (e.g., number and percentage of subjects). The number of events will also be presented except for summaries by highest category. The summary will include any AE, severity of AEs (highest category), investigator assessment of relationship of AEs to teduglutide, SAEs, and investigator assessment of relationship of SAEs to teduglutide.

Listings will include all the AEs and SAEs during the retrospective observation period. The ongoing AEs at the end of TED-C13-003 with the end dates are collected in the CRF and will be

Document: \\quintiles.net\Enterprise\Apps\sasdata\SASa\sas\Shire\Teduglutide\ZXA48914\Biostatistics\Documentation\Protocol\SHP633-303\_Retrospective\_SAP\_Final\_V1.0\_20171013  
Author: [REDACTED] Version Number: Final V1.0  
Version Date: 13Oct2017

Template No: CS\_TP\_BS016 – Revision 3  
Effective Date: 01May2012

Reference: CS\_WI\_BS005

Copyright © 2012 Quintiles Transnational Corp. All rights reserved.  
The contents of this document are confidential and proprietary to Quintiles Transnational Corp. Unauthorized use, disclosure or reproduction is strictly prohibited.

listed only.

#### **14.1.1. ALL AEs REPORTED DURING THE RETROSPECTIVE PERIOD**

Incidence of AEs will be presented by System Organ Class (SOC) and Preferred Term (PT) for all AEs reported during the retrospective period per protocol requirement, related AEs, SAEs, and related SAEs. Incidence will also be presented by SOC and PT for severity and maximum severity. Summaries by SOC and PT will present SOC in alphabetical order and PT within the SOC in descending order of incidence in the any teduglutide treatment group.

##### **14.1.1.1. Severity**

Severity is categorized as mild, moderate, or severe. Adverse events with a missing severity will be classified as severe. If a subject reports an AE more than once within that SOC/PT, summaries by severity will only provide the highest severity classification of the subject for the corresponding incidence summaries by SOC/PT.

##### **14.1.1.2. Relationship to Teduglutide**

Relationship, as indicated by the Investigator, is categorized as “*not related*” or “*related*”. A “*related*” AE is defined as an AE with a relationship of “*related*” to teduglutide. AEs with a missing relationship to teduglutide will be regarded as “*related*” to teduglutide.

#### **14.1.2. SERIOUS ADVERSE EVENTS**

Serious adverse events are those events recorded as “*Serious*” on the Adverse Events (Retrospective Period) Form of the eCRF. Any SAE that occurs from the time of the completion of core study TED-C13-003 through the signing of the retrospective ICF for the extension study will be captured. A summary of SAEs by SOC and PT will be prepared. A listing of SAEs will be presented as well.

#### **14.2. GROWTH DATA**

The last representative value for height and weight during each 12-week interval throughout the retrospective observation period will be captured in the Growth Data (Retrospective Period) form of eCRF as well as the head circumference for subjects 36 months of age and younger at the time the data was collected.

Document: \\quintiles.net\Enterprise\Apps\sasdata\SASa\sas\Shire\Teduglutide\ZXA48914\Biostatistics\Documentation\Protocol\SHP633-303\_Retrospective\_SAP\_Final\_V1.0\_20171013  
Author: [REDACTED] Version Number: Final V1.0  
Version Date: 13Oct2017

Template No: CS\_TP\_BS016 – Revision 3  
Effective Date: 01May2012

Reference: CS\_WI\_BS005

Copyright © 2012 Quintiles Transnational Corp. All rights reserved.  
The contents of this document are confidential and proprietary to Quintiles Transnational Corp. Unauthorized use, disclosure or reproduction is strictly prohibited.

The following growth data will be reported for retrospective observation period:

- Height (cm)
- Weight (kg)
- Head circumference (cm) for subjects  $\leq$  36 months of age

The following parameters will be derived during each 12-week interval:

- BMI ( $\text{kg}/\text{m}^2$ ) [when both height and weight are available in the interval]
- Height Z-score
- Weight Z-score
- BMI Z-score
- Head circumference Z-score for subjects  $\leq$  36 months of age

Descriptive statistics will be used to summarize growth data and derived parameters in actual value and change from baseline at 12-week intervals where associated parameters are collected. A mean  $\pm$  SE plot and a data listing will also be provided.

#### 14.2.1. GROWTH DATA SPECIFIC DERIVATIONS

- BMI

$\text{BMI} = 10000^* \text{ Body weight (kg)}/\text{body height (cm)}^2$ , where both body weight and body height data are available at the same scheduled interval

- Height, Weight, Head Circumference and BMI Z-scores

Official and validated SAS programs created by Centers for Disease Control and Prevention (CDC) will be used to calculate the Z-scores (standard deviations) for a child's sex and age (up to 20 years of age) for BMI, weight, height, and head circumference based on the CDC growth charts for children age 2 years and older and the WHO growth charts for infants and children  $<$  2 years of age. For more information on the CDC SAS programs, see [http://www.cdc.gov/growthcharts/computer\\_programs.htm](http://www.cdc.gov/growthcharts/computer_programs.htm).

Z-scores are calculated as the formula below:

$$\text{Z-score} = [((\text{observed value} / M) ^ L) - 1] / (S * L)$$

In which 'observed value' is the child's height, weight, head circumference or derived

Document: \\quintiles.net\Enterprise\Apps\sasdata\SASa\sas\Shire\Teduglutide\ZXA48914\Biostatistics\Documentation\Protocol\SHP633-303\_Retrospective\_SAP\_Final\_V1.0\_20171013  
Author: [REDACTED] Version Number: Final V1.0  
Version Date: 13Oct2017

Template No: CS\_TP\_BS016 – Revision 3  
Effective Date: 01May2012

Reference: CS\_WI\_BS005

Copyright © 2012 Quintiles Transnational Corp. All rights reserved.  
The contents of this document are confidential and proprietary to Quintiles Transnational Corp. Unauthorized use, disclosure or reproduction is strictly prohibited.

BMI. The L, M, and S values vary according to the child's sex and age. For more information on the LMS method, see <http://www.ncbi.nlm.nih.gov/pmc/articles/PMC27365/>.

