### 7.3. WINDOWING CONVENTIONS

Retrospective PS and growth data will be captured in 12-week intervals, with the first 12-week interval beginning at the TED-C13-003 EOS. There will be no windowing of scheduled intervals based on study day.

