### **12.1. EFFICACY ENDPOINTS**

#### **12.1.1. EFFICACY VARIABLES & DERIVATIONS**

PS investigator-prescribed data will be reported in the Parenteral Support (Retrospective Period) and Historical Teduglutide Treatment (Retrospective Period) eCRF. Data collected include weekly volume, calories, average days per week, and hours per day of prescribed PS. Prescribed data are the last representative PS prescription during each 12-week interval throughout the retrospective period, with the first 12-week interval beginning at the TED-C13-003 EOS visit, and at the beginning and end of any teduglutide treatment. Any tedgulutide was used in the 12-week interval will be indicated in the summary listing. The start date and end date of each 12-week interval will be derived based on the end of study date of TED-C13-003. The start date of the first 12-week interval will be the end of study date of TED-C13-003 + 1. The end date of the interval will be the start date of the interval + 12\*7. If the teduglutide

Document: \\quintiles.net\Enterprise\Apps\sasdata\SASa\sas\Shire\Teduglutide\ZXA48914\Biostatistics\Documentation\Protocol\SHP633-303\_Retrospective\_SAP\_Final\_V1.0\_20171013

Author: [REDACTED] Version Number: Final V1.0  
Version Date: 13Oct2017

Template No: CS\_TP\_BS016 – Revision 3  
Effective Date: 01May2012

Reference: CS\_WI\_BS005

Copyright © 2012 Quintiles Transnational Corp. All rights reserved.  
The contents of this document are confidential and proprietary to Quintiles Transnational Corp. Unauthorized use, disclosure or reproduction is strictly prohibited.

use period (from prescription start date to prescription stop date) falls into any 12-week intervals, the 12-week intervals will be marked 'Yes' in the teduglutide used column.

The calculation of average daily prescribed PS volume and caloric intake normalized to weight will follow the formula below:

Average daily value = (prescribed weekly PS parameter / 7) / last available weight prior to the 12-week interval.

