#### 18.7.1. VITAL SIGNS SPECIFIC DERIVATIONS

- BMI

BMI = 10000\* Body weight (kg)/body height (cm), where both body weight and body height data are available at the same scheduled visit

- Height, Weight and BMI Z-scores

Official and validated SAS programs created by Centers for Disease Control and Prevention (CDC) will be used to calculate the Z-scores (standard deviations) for a child's sex and age (up to 20 years of age) for BMI, weight, and height based on the CDC growth charts for children age 2 years and older and the WHO growth charts for infants and children < 2 years of age. For more information on the CDC SAS programs, see [http://www.cdc.gov/growthcharts/computer\\_programs.htm](http://www.cdc.gov/growthcharts/computer_programs.htm).

Z-scores are calculated as the formula below:

$$\text{Z-score} = [((\text{observed value} / M) ^ L) - 1] / (S * L)$$

In which 'observed value' is the child's height, weight or derived BMI. The L, M, and S values vary according to the child's sex and age. For more information on the LMS

Document: \\quintiles.net\Enterprise\Apps\sasdata\SASa\sas\Shire\Teduglutide\ZXA48914\Biostatistics\Documentation\SAP\SHP633-303\_SAP\_Draft\_V1.0\_20171023

Author: [REDACTED]

Version Number:

Draft V1.2

Version Date:

16Jan2018

Template No: CS\_TP\_BS016 – Revision 3

Reference: CS\_WI\_BS005

Effective Date: 01May2012

Copyright © 2012 Quintiles Transnational Corp. All rights reserved.

The contents of this document are confidential and proprietary to Quintiles Transnational Corp. Unauthorized use, disclosure or reproduction is strictly prohibited.

method, see <http://www.ncbi.nlm.nih.gov/pmc/articles/PMC27365/>.

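### Retrospective BMI may pair a height and a weight taken up to about 84 days apart, which can distort BMI and its Z-score in growing children

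*SAP*

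**What the plan says.** Retrospective data come from routine care: Section 4.1 describes them as "specific safety and efficacy measures that were completed in the course of" ordinary treatment between the end of the core study and consent to the extension. Section 14.2 then fixes what is kept: "The last representative value for height and weight during each 12-week interval throughout the retrospective observation period will be captured". BMI is among the parameters derived per interval, on the condition "when both height and weight are available in the interval". Section 14.2.1 repeats the condition: "where both body weight and body height data are available at the same scheduled interval".

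Section 12.1.1 sets the interval length: "The end date of the interval will be the start date of the interval" plus 12*7 days. Section 7.3, which covers both PS and growth data, adds: "There will be no windowing of scheduled intervals based on study day".

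The prospective SAP (Section 18.7.1) uses the same BMI formula but a narrower condition: "where both body weight and body height data are available at the same scheduled visit".

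The retrospective plan provides for very young children. Head circumference is captured "for subjects 36 months of age and younger at the time the data was collected", and Section 14.2.1 uses WHO charts below 2 years of age. BMI and BMI Z-score are summarised per interval as actual value and change from baseline, with a mean ± SE plot also planned for the growth data.

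**The concern.** BMI describes a child at one moment. A rule that asks only for the same 12-week interval lets a height from the start of the interval be combined with a weight from its end, or the reverse. Nothing else in the text narrows the gap. There is no windowing by day, and no study visit obliges routine care to measure both on one day.

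In an adult this would hardly matter. In a growing child the older value no longer fits the newer one, and height enters as a square. Baseline is the core-study baseline visit (Section 7.2), so a mismatch in a later interval does not cancel in the change from baseline. The plan also does not say which of two unequal dates supplies the age for the BMI Z-score. At stake is how accurately the BMI and BMI Z-score summaries describe nutritional status over the retrospective period.

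**Working it through.** The plan states no error size for this point, so there is no figure to reproduce. The check asks how far BMI can move under the rule as written.

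**Largest gap.** An interval runs from its start date to start + 12 × 7 = start + 84 days. Two values in one interval can therefore be up to 84 days (12 weeks) apart.

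**Formulas.** BMI = 10000 × weight (kg) / height (cm)², as in Section 14.2.1. Let H and W be the true height and weight at the later date, v_h and v_w the yearly gains, and t = gap in weeks / 52.18.

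- Older height: BMI error = (H / (H − v_h·t))² − 1
- Older weight: BMI error = −(v_w·t) / W
- Z shift ≈ ln(1 + error) / S, which is the SAP's LMS formula with L near 0

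**Assumptions.** The documents give no growth rates and no LMS values. H, W, v_h and v_w below are illustrative, and S (the coefficient of variation of BMI) is assumed to be 0.08 to 0.10.

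**Worked case.** For 18 months and a 12-week gap, t = 12 / 52.18 = 0.230.

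- Older height: (81 / (81 − 11 × 0.230))² − 1 = (81 / 78.47)² − 1 = +6.6%. The Z shift is ln(1.066) / 0.10 to ln(1.066) / 0.08, or about +0.63 to +0.79.
- Older weight: −(2.6 × 0.230) / 10.8 = −5.5%. The Z shift is about −0.57 to −0.71.

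**All cases** (BMI error, older height / older weight):

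| Assumed child | H; v_h | W; v_w | 4 weeks | 12 weeks |
|---|---|---|---|---|
| 9 months | 71 cm; 16 cm/yr | 8.8 kg; 4.5 kg/yr | +3.5% / −3.9% | +11.2% / −11.8% |
| 18 months | 81 cm; 11 cm/yr | 10.8 kg; 2.6 kg/yr | +2.1% / −1.8% | +6.6% / −5.5% |
| 24 months, slow growth | 82 cm; 5 cm/yr | 10.5 kg; 1.2 kg/yr | +0.9% / −0.9% | +2.9% / −2.6% |
| 30 months | 91 cm; 8.5 cm/yr | 13.2 kg; 2.2 kg/yr | +1.4% / −1.3% | +4.4% / −3.8% |
| 5 years | 109 cm; 6.5 cm/yr | 18 kg; 2.2 kg/yr | +0.9% / −0.9% | +2.8% / −2.8% |
| 10 years | 138 cm; 5.5 cm/yr | 32 kg; 3.5 kg/yr | +0.6% / −0.8% | +1.9% / −2.5% |

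Across the three toddler rows, the 12-week Z shift runs from about 0.3 SD (slow growth) to about 0.8 SD (18 months with an older height). With no gap, every entry is zero.

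**Residual error at a 7-day gap** (t = 1 / 52.18 = 0.0192). At 18 months an older height gives (81 / (81 − 0.211))² − 1 = +0.5%, and an older weight gives −0.050 / 10.8 = −0.5%. At 9 months the figures are (71 / (71 − 0.307))² − 1 = +0.9% and −0.086 / 8.8 = −1.0%.

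**The case against.** Several objections carry weight.

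- **The eCRF is not shown.** The growth form may record one common date for height and weight, and Section 4.2 refers the retrospective assessments to protocol sections that are not at hand. With one common date the mismatch could not arise. This stands as a limit on what can be claimed, but the SAP wording does not itself impose a common date.
- **The affected group is unknown.** Collection starts only after the core study ends, so infants may be few or absent. The plan provides for children up to 36 months but does not count them.
- **The consequence is limited.** Output is descriptive (Sections 7.4 and 8.4). Height and weight Z-scores do not depend on the pairing, and growth data are listed.
- **Setting BMI to missing loses data.** About 40 subjects are expected, and Section 8.3 wants all available data in the safety analysis. The loss is real, but only the derived BMI is withheld. The measured height and weight stay in.

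A reader might also draw three stronger conclusions that the document does not support.

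- **That BMI is wrong by several percent.** The error needs unequal dates, and reaching several percent needs a long gap in a young child.
- **That nutritional status will look too good.** This would follow if heights were usually the older values, for example because weight is measured more often. No section says so, and an older weight lowers BMI by a similar amount.
- **That the rule was carried over carelessly from the prospective SAP.** The retrospective SAP was final on 13 October 2017, and the first prospective draft is dated 23 October 2017.

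**Conclusion.** The point holds as a weakness in the stated rule, not as a demonstrated error in the results. As written, the retrospective SAP lets BMI combine values up to about 84 days apart, whereas the prospective SAP ties them to one visit.

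The possible distortion is large enough to matter for an individual toddler at a full-interval gap, modest at 4 weeks, and nil for same-day pairs. These sizes rest on assumed growth rates and an assumed BMI coefficient of variation, and slow growth brings them to the low end of the range. The effect on any interval mean cannot be stated, because neither the share of mismatched pairs nor the age mix is given. The direction is open as well.

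This is a minor point, worth correcting because the remedy is simple.

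**What to change.** In Sections 14.2 and 14.2.1 of the retrospective SAP:

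- Derive BMI and BMI Z-score only from a height and a weight measured on the same date, or within a short stated maximum gap. Seven days is one example, and under the assumptions above it leaves at most about 1% error even at 9 months.
- Use the common measurement date for age in the BMI Z-score. If a gap is allowed, state which of the two dates is used.
- Otherwise set BMI and its Z-score to missing for that interval.
- Show both measurement dates in the growth listing.
- Leave height Z-score and weight Z-score as they are.

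The cost is a sentence of SAP text and one date check in the derivation. The downside is that some intervals will have no BMI value. If the eCRF already forces one common date for both measurements, the rule removes nothing and costs nothing.
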